5.2 Exclusion Criteria

Individuals are not eligible for participation in this trial if any of the following criteria apply:

Target Disease	
1.	
Current DSM-5 diagnosis other than schizophrenia including, but not limited to, intellectual disability; schizoaffective disorder; major depressive disorder; schizopreniform disorder; psychotic depression; bipolar disorder; post-traumatic stress disorder; generalized anxiety disorder, obsessive compulsive disorder, eating disorders (bulimia, anorexia), or other anxiety disorders as a primary diagnosis (note: anxiety symptoms secondary to schizophrenia are allowed); delirium, dementia, amnestic, or other cognitive disorders.
 
Acute depressive symptoms within 30 days prior to signing the ICF that require treatment with an antidepressant are exclusory.
 
Acute manic symptoms within 30 days prior to signing the ICF that require treatment with a mood stabilizer are exclusory.
 
Additional excluded conditions include borderline, paranoid, histrionic, schizotypal, schizoid, or antisocial personality disorder.

2.	
Any of the following:
 
 • Schizophrenia considered resistant/refractory to antipsychotic treatment by history (failure to respond to 2 or more courses of adequate pharmacological treatment defined as an adequate dose per label and a treatment duration of at least 4 weeks) • History of response to clozapine treatment only or failure to respond to clozapine treatment for schizophrenia
3.	
Any of the following regarding history of schizophrenia:
 
 • Time from initial onset of schizophrenia <2 years based on prior records or participant self-report • Presenting with an initial diagnosis of schizophrenia • Presenting for the first time with an acute psychotic episode requiring treatment
4.	Reduction (improvement) in PANSS total score of $\geq 20\%$ between Screening and Baseline.
5.	
Either of the following:
 
 • History of tardive dyskinesia • Extrapyramidal symptoms that required medication within 6 months prior to signing the ICF
Other Medical History and Concurrent Conditions	
6.	
Current or past history of significant pulmonary, gastrointestinal, renal, hepatic, metabolic, genitourinary, endocrine (including diabetes mellitus), malignancy (except for basal cell carcinoma of the skin and cervical carcinoma in situ, at the discretion of the investigator), hematological, immunological, neurological, or psychiatric disease that, in the opinion of the investigator or medical monitor, could compromise either participant safety or the results of the trial.
 
Medical conditions that are minor or well-controlled may be considered acceptable if the condition does not expose the participant to an undue risk of significant AEs or interfere with the assessment of safety or efficacy during the course of the trial. The medical monitor should be contacted in any instance where the investigator is uncertain regarding the stability of a participant's medical condition(s) and the potential impact of the condition(s) on trial participation.

7.	
Current or past history of significant cardiovascular disease including any of the following: ischemic heart disease, myocardial infarction, cardiac valvulopathy, cardiac surgery revascularization (coronary artery bypass grafting) or stenting or percutaneous transluminal coronary angioplasty, receiving more than 2 medications to treat hypertension or have not been on stable doses of antihypertensive medications for >3 months, orthostatic hypotension, angina, unstable angina, cerebrovascular accident or stroke or transient ischemic attack, pacemaker, atrial fibrillation, atrial flutter, paroxysmal atrial tachycardia, or non-sustained or sustained ventricular tachycardia, pulmonary arterial hypertension, sick sinus syndrome, Type 2 second-degree or third-degree atrioventricular block, congestive heart failure, personal or family history of sudden death or long QT syndrome, unexplained syncope, syncope within the last 3 years regardless of etiology, or symptomatic orthostatic dizziness (by history or observed at the Screening Visit during the vital sign assessments).

8.	
Active central nervous system infection, demyelinating disease, degenerative neurological disease, mental retardation, brain tumor, prior hospitalization for severe head trauma, seizures (excluding febrile seizures in childhood), or any central nervous system disease deemed to be progressive during the course of the trial that may confound the interpretation of the trial results.

9.	
Diagnosis of moderate to severe substance or alcohol-use disorder (excluding nicotine or caffeine) as per DSM-5 criteria within 12 months prior to signing the ICF.
 
Participants with mild substance or alcohol-use disorder may be included in the trial following consultation and approval by the medical monitor.

10.	
“Yes” responses for any of the following items on the C-SSRS (within the past 6 months):
 
 • Suicidal Ideation Item 4 (Active Suicidal Ideation with Some Intent to Act, without Specific Plan) • Suicidal Ideation Item 5 (Active Suicidal Ideation with Specific Plan and Intent) 
“Yes” responses for any of the following items on the C-SSRS (within past 2 years):
 
 • Any of the Suicidal Behavior items (Actual Attempt, Interrupted Attempt, Aborted Attempt, Preparatory Acts or Behavior) 
Serious risk of suicide in the opinion of the investigator is also exclusionary.

11.	
Any condition or surgery that could possibly affect drug absorption, including, but not limited to, complicated appendectomy or cholecystectomy, bowel resections, bariatric weight loss surgery, gastric banding, or gastrectomy.

12.	
Have recently been diagnosed with and hospitalized for symptomatic COVID-19 or test positive for SARS-CoV-2 at Screening.

Prior or Concomitant Therapies	
13.	
Use of prohibited medications prior to randomization within the required wash-out period (Table 4) or likely to require prohibited concomitant therapy (Table 5) during the trial.

14.	
Transcranial magnetic stimulation or electroconvulsive therapy within 90 days of signing the ICF.

Laboratory Test Results	
15.	
Positive result for HIV antibody, hepatitis B surface antigen, or hepatitis C antibody with detectable viral RNA levels at Screening.
 
Note: Positive or indeterminate test result for hepatitis C antibody should follow with hepatitis C virus PCR RNA test. If result is positive, the participant is excluded.

16.	
Positive drug screen or a positive test for alcohol (note: individuals who test positive for alcohol may be rescreened).
 
Participants with a positive urine drug screen resulting from use of marijuana (any THC-containing product), prescription, or over-the-counter medications or products that, in the investigator's documented opinion, do not signal a clinical condition that would impact the safety of the participant or interpretation of the trial results may continue evaluation for the trial following consultation and approval by the medical monitor.

17.	
Any of the following clinical laboratory test results at the Screening Visit, confirmed by a single repeat measurement, if deemed necessary:
 
 • AST or ALT $\geq 2 \times$ ULN • Total bilirubin $>1.5 \times$ ULN. If Gilbert's syndrome is suspected, total bilirubin $>1.5 \times$ ULN is acceptable if the conjugated or direct bilirubin fraction is $<20\%$ of total bilirubin
18.	
Positive pregnancy test result prior to receiving IMP.
 
Note: female participants who are pregnant, breastfeeding, or planning to become pregnant during IMP treatment or within 7 days after the last dose of IMP are also excluded.

Other Exclusionary Safety Assessments	
19.	
12-lead ECG demonstrating any of the following at the Screening Visit and at Baseline:
 
 • QTcF interval >450 ms • QRS interval >120 ms (unless right bundle branch block) • PR interval >200 ms • LVH with ST depressions and/or T wave inversions in leads with relatively tall R waves (ie, LVH with associated ST-T wave abnormalities) • Type 2 second-degree or third-degree atrioventricular block • Heart rate <45 bpm or >100 bpm • Abnormal ECG changes (such as clinically significant ST depression or elevation or T wave inversion) • Abnormal heart rhythm (atrial fibrillation and atrial flutter) 
Note: at Screening, eligibility will be based on the average of a centrally read triplicate set of ECGs.
 
At Baseline Visit, if any of the above criteria are met on the machine read of the ECG, the medical monitor should be consulted to determine whether the participant is eligible for randomization.
 
The medical monitor should be contacted in any instance where the investigator is uncertain regarding the interpretation of ECG results.

20.	
Blood pressure measurements demonstrating any of the following at the Screening Visit and/or at Baseline:
 
 • Systolic blood pressure ≥ 140 mmHg and/or diastolic blood pressure ≥ 90 mmHg 
 ◦ Blood pressure will be measured in triplicate at approximately 1-minute intervals in a supine position after at least 3 minutes of rest. The triplicate measures will be individually recorded and the average of the last 2 measurements will be used to determine eligibility. • Orthostatic hypotension, defined as a decrease of ≥ 20 mmHg in systolic blood pressure and/or ≥ 10 mmHg in diastolic blood pressure after at least 2 minutes of standing compared with the average of the resting supine blood pressure measurements as measured above
21.	
Any other abnormal safety findings unless, based on the investigator's judgment, the findings are not medically significant and would not impact the safety of the participant or the interpretation of the trial results. The medical monitor should be contacted to discuss individual cases, as needed.
 
Tests with abnormal results that are potentially exclusionary should be repeated to ensure reproducibility of the result before excluding a potential participant based on criteria provided in the protocol.

Lifestyle or Other Miscellaneous Exclusion	
22.	Refusal to abstain from grapefruit-containing foods or beverages or Seville orange-containing foods or beverages from 7 days prior to dosing through Week 6/ET.
23.	Chronic consumption of >400 mg/day of caffeine-containing drinks or food (eg, >4 cups [8 ounces] of brewed coffee, 9 cans [12 ounces] of diet cola, 12 cans [12 ounces] of cola, 8.5 cups of brewed black tea, 2 energy shot drinks) based on participant self-report.
24.	Considering or scheduled to undergo any surgical procedure during the trial.
25.	Prisoners or participants who are compulsorily detained (involuntarily incarcerated) for treatment of either a psychiatric or physical illness (eg, infectious disease).
26.	Any other condition that would preclude IMP administration or trial participation (eg, difficulty swallowing, poor venous access).
27.	Known allergy or hypersensitivity to emraclidine, closely related compounds, or any of its specified ingredients.
28.	Received IMP in a prior clinical trial of emraclidine.
29.	
History of participation in any clinical trial involving an IMP as defined by the following:
 
 • Current enrollment or past participation within 90 days prior to signing the ICF, with the exception of a trial with a long-term follow-up period where dosing occurred more than 12 months prior to signing the ICF for this trial (discussion with and approval by the medical monitor required prior to enrollment) • Enrollment in more than 1 interventional trial within 12 months prior to signing the ICF 
Note: Prior participation in an interventional trial and a rollover extension trial with the same IMP within the last 12 months is permitted

30.	Anyone who should not participate in the trial in the opinion of the sponsor, investigator, or medical monitor, eg, participants who would be considered a risk for violent or destructive behavior.

31.	Employee of the investigator, clinic, or sponsor with direct involvement in the proposed trial or other trials under the direction of the investigator or clinic, as well as family members of the employee or investigator.
-----	--

Abbreviations: AE=adverse event; ALT=alanine aminotransferase; AST=aspartate aminotransferase; C-SSRS=Columbia-Suicide Severity Rating Scale; DSM-5=Diagnostic and Statistical Manual of Mental Disorders, Fifth Edition; ECG=electrocardiogram; ET=early termination; HIV=human immunodeficiency virus; ICF=informed consent form; IMP=investigational medicinal product; LVH=left ventricular hypertrophy; PANSS=Positive and Negative Syndrome Scale; QTcF=QT interval corrected for heart rate using Fridericia's formula; THC=tetrahydrocannabinol; ULN=upper limit of normal range.

5.3 Lifestyle Considerations

5.3.1 Meals and Dietary Restrictions

Participants should fast for at least 8 hours prior to screening safety laboratory evaluations, if at all possible. If this is not possible, nonfasting screening laboratory evaluations may be obtained for eligibility determination. Participants must fast for a minimum of 8 hours prior to baseline and Week 6 safety laboratory assessments and should avoid consuming high-fat meals for 8 hours prior to any other safety laboratory assessments.

Participants should refrain from eating or drinking food/food products which are strong/moderate inhibitors of cytochrome P450 3A4 (including but not limited to grapefruit, grapefruit juice, or grapefruit-related citrus fruits/juices [eg, Seville oranges, pomelos]) from 7 days prior to dosing through Week 6/ET.

5.3.2 Caffeine, Alcohol, and Tobacco

Chronic consumption of >400 mg/day of caffeine-containing drinks or food (eg, >4 cups [8 ounces] of brewed coffee, 9 cans [12 oz] of diet cola, 12 cans [12 oz] of cola, 8.5 cups of brewed black tea, 2 energy shot drinks) will be prohibited while participants are in the inpatient facility.

Participants should abstain from alcohol from time of signing ICF (check-in to inpatient facility) until Week 6/ET (check-out of inpatient facility). Participants will undergo an alcohol breath test at Screening (check-in), upon return to the inpatient facility if they leave, and at the discretion of the investigator.

For participants who smoke, the number of cigarettes (or equivalent) smoked per day will be collected at both Screening and Baseline.

5.3.3 Activity

Participants should abstain from strenuous exercise during the trial.

5.4 Screen Failures

Screen failures are defined as participants who consent to participate in the clinical trial but are not subsequently randomly assigned to IMP. A minimal set of screen failure information is required to ensure transparent reporting of screen failure participants to meet the Consolidated Standards of Reporting Trials publishing requirements and to respond to queries from health authorities. Minimal information includes demography, screen failure details, and eligibility criteria.

Individuals who do not meet the criteria for participation in this trial (screen failure) at screening may be rescreened once at the discretion of the investigator and after consultation with the medical monitor unless screen failure is due to a positive urine drug screen for illicit substances. Rescreened participants will be assigned a new participant number.

6 TRIAL INTERVENTION AND CONCOMITANT THERAPY

Trial intervention is defined as any investigational intervention(s), marketed product(s), placebo, or medical device(s) intended to be administered to a trial participant according to the trial protocol.

In this protocol, the trial interventions are referred to as IMPs. An IMP is a pharmaceutical form of an active substance or placebo being tested or used as a reference in a clinical trial, including products already with a marketing authorization but used or assembled (formulated or packaged) in a way different from the authorized form, or when used for an unauthorized indication, or when used to gain further information about the authorized form.

6.1 Trial Interventions Administered

A summary of the IMP to be administered during this trial is presented in [Table 3](#).

Table 3 **Investigational Medicinal Product**

Treatment Group	Emraclidine 15 mg QD	Emraclidine 30 mg QD	Placebo
Type	Drug	Drug	Not applicable
Dose Formulation	Tablet	Tablet	Matching tablet
Unit Dose Strength	15 mg	30 mg	0 mg
Dosage Level	15 mg QD	30 mg QD	0 mg QD
Route of Administration	Oral	Oral	Oral
Sourcing	Provided centrally by the sponsor	Provided centrally by the sponsor	Provided centrally by the sponsor
Packaging and Labeling	IMP will be provided in bottles. Each bottle will be labeled as required per US requirement.	IMP will be provided in bottles. Each bottle will be labeled as required per US requirement.	Trial treatment will be provided in bottles. Each bottle will be labeled as per country requirement.

Abbreviations: IMP=investigational medicinal product; QD=once daily; US=United States.

Information regarding potential overdose with IMP is provided in [Section 8.3.6](#).

6.2 Preparation, Handling, Storage, and Accountability

The investigator or designee must confirm appropriate temperature conditions have been maintained during transit (original shipment and/or moving of IMP supply from 1 office or facility to another within the trial site's network) for all IMP received and any discrepancies are reported and resolved before use of the IMP.

Only participants enrolled in the trial may receive IMP and only authorized trial site staff may supply or administer IMP. All IMP must be stored in a secure, environmentally controlled, and monitored (manual or automated) area in accordance with the labeled storage conditions with access limited to the investigator and authorized trial site staff.

The investigator is responsible for IMP accountability, reconciliation, and record maintenance (ie, receipt, reconciliation, and final disposition records).

Further guidance and information for the preparation, handling, storage, accountability, and disposition of unused IMP are provided in the pharmacy manual.

6.3 Measures to Minimize Bias: Randomization and Blinding

6.3.1 Participant Assignment to Treatment

All participants will be centrally randomized in a 1:1:1 ratio to 1 of 3 treatment groups (placebo, emraclidine 15 mg QD, or emraclidine 30 mg QD) on Day 1 via an IRT

according to a computer-generated randomization scheme. Participants will be sequentially assigned to the next available randomization number and will receive the IMP that corresponds to that randomization number. Once a randomization number has been assigned, it will not be reassigned.

The randomization will be stratified by geographic region with 2 strata: United States or all other countries.

6.3.2 *Blinding*

During the entire trial, treatment will be blinded such that participants, the sponsor/designee, raters for clinician-administered scales, the investigator, and other site and trial personnel will not have knowledge of the treatment assignment at any visit. Access to the treatment codes will be restricted to personnel who are responsible for generating and maintaining the randomization code, packaging the IMPs, operating the IRT, analyzing the PK blood samples, or reporting SAEs or AESI to regulatory agencies.

At the initiation of the trial, investigators and site personnel will be instructed on the method for breaking the blind. In case of an emergency, the investigator has the sole responsibility for determining if unblinding of the treatment assignment for an individual participant is warranted. Participant safety must always be the first consideration in making such a determination. If the investigator decides that unblinding is warranted, the investigator should make every effort to contact the medical monitor before unblinding a participant's treatment assignment unless this could delay emergency treatment of the participant. The medical monitor must be notified within 24 hours after breaking the blind for a trial participant.

Documentation of unblinding should be recorded in the participant's medical record, including the reason for breaking the blind, the date and time the blind was broken, and the names of the personnel involved. Once the blind is broken for a participant, treatment with the IMP may not be reinitiated for that participant.

6.4 Trial Intervention Compliance

The date and dose (and time on days with PK assessments) of each IMP administration, along with information on any missed or inappropriately administered dose, will be recorded in source documents and the eCRF. Compliance will be ensured by a hand and mouth check during the oral dosing administration.

6.5 Dose Modification

No dose modifications are permitted during the trial.

6.6 Intervention After the End of the Trial

Participants who complete through Day 45 of the trial may have the opportunity to receive open-label treatment with emraclidine in an open-label extension trial

(Protocol CVL-231-2003) if available. Participants who are ineligible or elect not to enter the open-label extension trial will resume treatment with available antipsychotic medications at the discretion of and as determined by their physician.

6.7 Prior and Concomitant Therapy

6.7.1 Time Period for Recording Prior and Concomitant Therapy

The investigator will record all therapies (including vaccines, over-the-counter or prescription medicines, vitamins, and/or herbal supplements) taken by the participant from 30 days prior to signing the ICF through the end of the evaluation period (defined as the time period during which participants are evaluated for primary and/or secondary objectives).

For concomitant medications, the following will be recorded in the eCRF: medication, indication, dose, frequency, route, start date and end date. For concomitant therapy, the following will be recorded in the eCRF: therapy, indication, start date, and end date.

The medical monitor should be contacted if there are any questions regarding concomitant or prior therapy.

6.7.2 Prohibited Therapy

All participants must agree to discontinue all prohibited medications during the Screening Period in order to meet the protocol-specified washout periods. [Table 4](#) provides the required duration of washout for selected prohibited medications. All other prohibited medications must be discontinued at least 24 hours before the first dose of IMP.

Table 4 List of Medications Prohibited Before Randomization

Prohibited Prior Medications	Washout (if applicable)
Antipsychotic agents	
Oral (or immediate-release intramuscular) aripiprazole or cariprazine	14 days
Other oral (or immediate-release intramuscular) antipsychotic agents	7 days
Depot or long-acting injectable antipsychotic agents	1.5 cycles (per prescribing information)
Antidepressants	
Fluoxetine or Symbax	28 days
Monoamine oxidase inhibitors	14 days
Citalopram and escitalopram	7 days
Venlafaxine and desvenlafaxine	7 days
All other antidepressants	14 days
Mood stabilizers (ie, lithium and/or anticonvulsants)	14 days
All other psychoactive substances (except benzodiazepines)	7 days
Varenicline (eg, Chantix)	7 days
Beta receptor antagonists to treat hypertension	Not applicable
Other antihypertensive agents	Not applicable
Receiving more than 2 medications to treat hypertension	
Have not been on stable doses of antihypertensive medications for >3 months	

[Table 5](#) lists all medications prohibited during the trial, including exceptions, where appropriate.

Table 5 List of Medications Prohibited During the Treatment Period

Psychotropic agents including, but not limited to, the following:
a) Antipsychotics, including depot or long-acting injectable formulations
b) Antidepressants (including monoamine oxidase inhibitors)
c) Mood stabilizers (ie, lithium and/or anticonvulsants)
d) Benzodiazepines, except specific benzodiazepines when used to treat anxiety, agitation, or insomnia secondary to schizophrenia ^a
e) Prescription stimulants (including appetite suppressants and treatments for attention-deficit hyperactivity disorder or narcolepsy)
f) Opioid analgesics, unless approval is obtained from the medical monitor. Approval for opioid use may be considered for a documented and clinically appropriate indication (eg, episodic pain, tooth extraction) if prescribed at a medically appropriate dose and frequency
Hypnotics, including ramelteon and other non-benzodiazepine sleep aids, except for specific medications when used to manage active insomnia ^b
Antihistamines (except for loratadine and cetirizine)
Varenicline (eg, Chantix)
Vitamins, other nutritional supplements, and non-prescription herbal preparations, unless approved in advance by the medical monitor
Investigational agents

Any drug or product that is a moderate to strong inducer of CYP3A metabolism, which has the potential to lower emraclidine exposure levels. An example list of strong (>80% reduction in AUC) and moderate (50% to 80% reduction in AUC) inducers is provided in [Section 10.7](#). Previous use of a CYP3A inducer must not have been taken at least 8 weeks prior to dosing.

Any drug or product that is classified as a significant (ie, strong or moderate) inhibitor of the CYP3A metabolic pathway, which has the potential to increase emraclidine exposure levels. An example list of strong (eg, >5-fold increase in AUC) and moderate (eg, 2-to 5-fold increase in AUC) inhibitors is provided in [Section 10.7](#). Previous use of a significant inhibitor of CYP3A must not have been taken for at least 2 weeks prior to dosing.

Participants taking a drug that is a substrate for the renal transporters OCT2, MATE1, and MATE2K (eg, metformin).

Anticholinergic agents, beta-receptor antagonists (eg, propranolol), and VMAT2 inhibitors (eg, valbenazine and deutetabenazine).

Initiation or change in antihypertensive therapy is prohibited during the trial unless discussed with and approved by the medical monitor.

Abbreviations: AUC=area under the concentration-time curve; CYP=cytochrome P450; MATE=multidrug and toxin extrusion transporter; OCT=organic cation transporter; VMAT2=vesicular monoamine transporter 2.

- a. See [Section 6.7.3](#) for details on benzodiazepine use during the trial.
- b. See [Section 6.7.4](#) for details on non-benzodiazepine sleep aid use during the trial.

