10.7 Moderate to Strong Inducers and Inhibitors of Cytochrome P450 3A (not exhaustive)

Note that this is not a complete list and that the investigator is responsible for ensuring that participants are not receiving any strong or moderate inducers or inhibitors of cytochrome P450 3A during the trial.

CYP 3A Inhibitors/

CYP 3A Inducers

Antivirals	Antivirals
Nirmatrelvir/ritonavir ^a	Efavirenz
Indinavir	Nevirapine
Nelfinavir	Etravirine
Ritonavir	Tipranavir
Saquinavir	Miscellaneous
Boceprevir	Barbiturates
Lopinavir/ritonavir	Carbamazepine
Amprenavir	Cenobamate
Atazanavir	Eslicarbazepine
Telaprevir	Glucocorticoids (systemic)
Darunavir/ritonavir	Modafinil
Fosamprenavir	Oxcarbazepine
Antibiotics	Phenobarbital
Clarithromycin	Phenytoin
Erythromycin	Rifabutin
Telithromycin	Rifampin
Ciprofloxacin	St. John's wort
Anti-infectives	Bosentan
Itraconazole	
Ketoconazole	
Fluconazole	
Posaconazole	
Voriconazole	
Anti-anginal/hypertensive therapy	
Diltiazem	
Verapamil	
Anti-cancer therapy	
Crizotinib	
Imatinib	
Miscellaneous	
Nefazodone	
Aprepitant	
Grapefruit juice ^b	
Conivaptan	

- a. Paxlovid (nirmatrelvir co-packed with ritonavir) is prohibited.
- b. A 7-day washout prior to dosing is required if grapefruit juice was being consumed continually.

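### Section 6.7.2 gives CYP3A inducers and inhibitors washouts that do not agree, and for washout Exclusion 13 points only to the table that lacks the CYP3A limits

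*Protocol*

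**What the plan says.** - **Protocol 6.7.2, text.** Table 4 "provides the required duration of washout for selected prohibited medications". For the rest, "All other prohibited medications must be discontinued at least 24 hours before the first dose of IMP".
- **Protocol 6.7.2, Table 4** (headed for the period before randomization). It has no CYP3A row. Mood stabilizers, with anticonvulsants named, have 14 days. Psychoactive substances not listed elsewhere, benzodiazepines excepted, have 7 days.
- **Protocol 6.7.2, Table 5** (headed for the Treatment Period). For inducers: "Previous use of a CYP3A inducer must not have been taken at least 8 weeks prior to dosing". For strong or moderate inhibitors: "Previous use of a significant inhibitor of CYP3A must not have been taken for at least 2 weeks prior to dosing". The inducer sentence is awkward; I read it as no use within the 8 weeks before dosing.
- **Protocol 5.2, Exclusion 13.** It bars "Use of prohibited medications prior to randomization within the required wash-out period (Table 4"), and then cites Table 5 for a different purpose: participants likely to need prohibited therapy during the trial.
- **Protocol 10.7.** The inducer list includes carbamazepine, oxcarbazepine, eslicarbazepine, phenytoin, phenobarbital, cenobamate and modafinil. Grapefruit juice is listed as an inhibitor, with the note "A 7-day washout prior to dosing is required if grapefruit juice was being consumed continually".
- **Protocol 6.7.1 and 4.1.1.** Prior therapy is recorded from 30 days before consent. Screening lasts up to 15 days, or 21 with approval.

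**The concern.** The same drug can be acceptable under one stated rule and barred under another, with nothing to say which governs. A site checking prior use would naturally go to Table 4, because its heading covers the period before randomization and Exclusion 13 sends the reader there. The CYP3A limits sit in the table headed for the Treatment Period. Sites could therefore decide differently about the same patient.

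Table 5 gives the reason for the limits: inducers have the potential to lower emraclidine exposure and inhibitors to raise it. Section 4.3 says the two fixed doses are meant to show how effects vary with exposure, and the PK parameters in SAP 5.16.2 come from Day 24. A participant admitted on the shorter rule contributes data from a period that the protocol elsewhere treats as too close to the interacting drug. It is also unclear whether such a participant counts as a protocol deviation.

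**Working it through.** No figure in the plan depends on this point, so the check is a comparison of texts plus day arithmetic.

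**1. Which washout applies to each drug**

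| Drug | Shorter rule | Table 5 |
|---|---|---|
| Inducer with no Table 4 row (eg, rifampin) | 24 hours | 8 weeks |
| Modafinil, if read as a psychoactive substance | 7 days (Table 4) | 8 weeks |
| Carbamazepine and other anticonvulsant inducers | 14 days (Table 4) | 8 weeks |
| Inhibitor with no Table 4 row (eg, clarithromycin) | 24 hours | 2 weeks |
| Grapefruit juice | 7 days (10.7, 5.3.1, Exclusion 22) | 2 weeks, if covered by its general drug-or-product wording |

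**2. Eligibility example.** Carbamazepine stopped 15 days before dosing: 15 > 14, so Exclusion 13 is passed; 15 < 56, so Table 5 is breached.

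**3. Gap and duration.** Let *w* be the days from last intake to Day 1 and *L* the Table 5 limit (56 or 14 days).

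Shortfall = *L* − *w*. First study day outside the window = 1 − *w* + *L*.

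| Class | *w* | Shortfall | First study day outside |
|---|---|---|---|
| Inducer (*L* = 56) | 1 | 55 | Day 56 |
| Inducer | 7 | 49 | Day 50 |
| Inducer | 14 | 42 | Day 43 |
| Inhibitor (*L* = 14) | 1 | 13 | Day 14 |
| Inhibitor | 7 | 7 | Day 8 |
| Inhibitor | 14 | 0 | Day 1 |

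For an inducer stopped exactly at the shorter limit, the Day 4 and Day 24 PK samples and the nominal Day 42 PANSS all fall inside the 8-week window. At the 14-day limit this is close: the window ends at Day 43, and for the 15-day example it ends at Day 42 (1 − 15 + 56). For inhibitors the window touches Day 4 PK and Week 1, not Week 6.

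**4. Can the 8-week rule be checked?** The longest required look-back before dosing is 30 + 15 = 45 days, or 30 + 21 = 51 days with extended screening. Against 56 days, at least 11 or 5 days are not covered by the required record.

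**5. Effect on power (illustration).** The plan's own figure comes first: with 93 per arm and effect size 0.48, power = Φ(0.48 × √(93/2) − 1.96) = Φ(1.313) = 90.5%, which agrees with the stated 90% or more. Now suppose a share *f* of the active arm has no effect at all, so that the effect size becomes 0.48 × (1 − *f*):

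| *f* (assumed) | Power |
|---|---|
| 1% | 90.0% |
| 2% | 89.4% |
| 5% | 87.5% |
| 10% | 83.8% |

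The documents give no value for *f*, and zero effect is a pessimistic assumption.

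**The case against.** The strongest reply is that the texts can be read together. The 24-hour sentence sets a minimum, so a site that follows Table 5 satisfies both. A specific rule normally prevails over a general one, and Table 5 stands in the same section. Inclusion 7 asks for willingness to meet the protocol's washouts without limiting them to Table 4. Section 8 allows no waivers, and 6.7.1 sends questions on prior therapy to the medical monitor. This stands as far as it goes: a careful site can comply with everything. But the protocol never says that Table 5 governs, and for anticonvulsants the Table 4 row is itself specific, so that principle does not settle the matter.

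Several stronger readings are tempting and are not supported:

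- *Exclusion 13 ignores Table 5.* It cites Table 5, but only for likely need during the trial. The gap is confined to washout.
- *Every overlap is a conflict.* Nefazodone, an antidepressant, has 14 days in Table 4, which equals the 2-week inhibitor limit. Grapefruit has a consistent 7 days in three places, one of them its own eligibility criterion; only Table 5's general wording differs.
- *The 30 mg arm would behave like 15 mg, or like a much higher dose.* This needs the full interaction to persist after the drug is stopped. The documents give no carry-over data, and Section 2.2.3 says that high AUC variability hampered the assessment of dose proportionality.
- *Many participants are exposed.* The documents give no prevalence. Exclusion 1 (bipolar disorder, schizoaffective disorder, recent mania needing a mood stabilizer) and Exclusion 8 (seizures) remove common reasons for taking these anticonvulsants. In the placebo group there is no emraclidine exposure to alter.

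**Conclusion.** The inconsistency is real and lies in the current text. One stated rule admits participants whom another stated rule bars, the eligibility criterion follows the table without the CYP3A limits, and the required medication record is too short to confirm the 8-week limit. The clearest case is the anticonvulsant inducers, at 14 days against 8 weeks; drugs caught only by the 24-hour sentence are more a matter of unstated precedence. Grapefruit is a secondary wording mismatch.

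The size is known in days, not in participants or exposure. A trial-level loss of efficacy or a safety effect should not be inferred; the effect on power is likely small unless the affected share is far larger than the exclusions suggest. The case for acting rests on consistent eligibility decisions and interpretable PK data, and the correction is cheap. The conclusion assumes that 8 weeks means no inducer use in the 56 days before dosing, and that sites take prior-use washouts from the table Exclusion 13 names.

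**What to change.** The sponsor must reconcile the 24-hour sentence, Table 4, Table 5, Section 10.7 and Exclusion 13. No washout length is proposed here. After reconciliation:

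1. One washout applies to each CYP3A class, inducers and inhibitors.
2. The text states which entry governs a drug that falls under two, such as the anticonvulsants, modafinil and grapefruit.
3. Exclusion 13 refers to wherever those washouts are stated.
4. The look-back for prior therapy in 6.7.1 is aligned with the rule kept, so that compliance can be checked from the record.
5. Participants randomized inside the reconciled window are flagged in the deviation review that SAP 5.17 already schedules before unblinding.

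The cost is protocol wording in 5.2, 6.7.1, 6.7.2 and 10.7, an eligibility checklist update, and a small change in screen failures in one direction or the other, depending on the rule kept.
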